3. SYNOPSIS

Study Title	A prospective randomised controlled study assessing the impact of simulation training in primary total hip replacement (THR).
Short title	THR Performance & Assessment
Study registration	IRAS Project ID: 270167 6th August 2019
Sponsor	University of Oxford/Clinical Trials and Research Governance Joint Research Office, [name]

Funder	Dinwoodie Charitable Company		
Study Design	Prospective randomised controlled study, with an additional comparator group.		
Study Participants	
Trauma & Orthopaedic Specialty Registrars (intervention and control groups), Consultant Orthopaedic Surgeons, and Arthroplasty Fellows.
 
Patients undergoing elective primary THR at the 2 named NHS Hospitals in this study, when their lead surgeon is enrolled as a participant in this study.
		
Participant Sample Size	
Surgeon participant Group 1 a: Interventional group ('StR's'): Thames Valley Deanery Trauma & Orthopaedic Specialty Registrars on Arthroplasty clinical placements (n=8) receiving additional training
 
Surgeon participant Group 1 b: control group (StR's): Thames Valley Deanery Trauma & Orthopaedic Specialty Registrars on Arthroplasty clinical placements receiving routine and normal Deanery training only (n=8).
 
Surgeon participant Group 2: ('Experts & Fellows'): Consultant Orthopaedic Surgeons (n=5), and nationally appointed Arthroplasty Fellows (n=8).
 
Patient Participants: Estimated total n= 193, calculated on the basis of outcomes data following THR to be collected for:
 
 8 patients per Specialty Registrar (n = 128) 5 patients per Fellow (n = 40) 5 patients per Consultant (n = 25) 		
Planned Study Period	
Total length of project = 18-24 months
 
Length of individual participants involvement = 6 months
		
Planned Recruitment period	
Start date for recruitment = August 2019
 
End date for recruitment = February 2021 (with possible extension to August 2021)
		
	Objectives	Outcome Measures	Timepoint(s)

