6. OBJECTIVES AND OUTCOME MEASURES

Objectives	Outcome Measures	Timepoints of evaluation
Primary To assess the impact of simulation training on surgical trainee performance and patient outcomes following THR.	Participants: 
 Wireless motion data metrics from elbow worn sensors (hand movements, path length and time taken) Global Rating Scales (GRS). Objective Structured Assessment of Technical Skills (OSATS). Surgical checklists. Patients: 
 X-ray analysis of THR.[4] Blood loss and transfusion rates. Peri-operative patient morbidity In-patient length of stay. PROMs: EQ-5D and OHS. 	Intra-operative assessments to be performed at a minimum of 8 separate THR operations for each participant in Group 1 (StR'S) over a 6-month period. Outcome measures data will be collected for all patients who have had a THR performed by any participant as the lead surgeon in this study.
Secondary To define an expert standard when performing a primary elective THR. To determine if operative surgeon performance metrics during a THR relate to surgical experience, or patient outcomes.	Participants: 
 Wireless motion data metrics from elbow worn sensors (hand movements, path length and time taken) Patients: 
 X-ray analysis of THR.[4] Blood loss and transfusion rates. Peri-operative patient morbidity In-patient length of stay. PROMs: EQ-5D and OHS. 	Intra-operative assessments at a minimum of 5 separate THR operations for each participant in Group 2 (Experts & Fellows). Outcome measures data will be collected for all patients who have had a THR performed by any participant as the lead surgeon.

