- 2b): Good overall with minor imperfections on femoral side.
- 3: Moderate concerns but does not require revision surgery.
- 4: Significant concerns requiring revision surgery.

Every patients post-operative x-ray will also be reviewed by the PI ([name]) for acetabular component positioning (inclination and version) using the methodology described by Bachhal [4]. This continuous data will be assessed for normality of distribution, and analysed using similar methodology as described above for the motion data. We will be looking for any statistically significant differences between the 2 groups of participants, within the two sub-groups of StR's (control and intervention), and also within the intervention sub-group in order to compare performance before and after additional training.

Other outcomes data:

Following collection of the outcome measures listed below, the normality of the data distribution will be checked with the Shapiro-Wilk test. Descriptive statistics will be used to outline the central tendency and variation of these data sets. Statistical analyses between each group of participants will be performed using either the parametric unpaired t-test or a non-parametric Mann-Whitney U test depending on the distribution of the data. Subsequent analysis of the outcomes data using a paired t-test, or Mann-Whitney U test will also be performed within the two sub-groups of the StR's (control and intervention), and also within the intervention sub-group in order to compare outcomes before and after additional training.

- Theatre time usage.
- Blood loss (pre-/post-op haemoglobin levels)
- In-patient length of stay.
- PROMs: EQ-5D and OHS.

The Chi-squared test (or Fishers exact test if the sample is <5) will be used to determine any significant differences between the groups regarding the incidence of blood transfusions or peri-operative morbidity.

All of these tests will be performed using the SPSS statistical package, which is available for any registered student on the University of Oxford current Licencing agreement.

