12 DATA MANAGEMENT

Within this study both patients and participants will have all of their personal data anonymised via the use of Unique Patient or Participant Identifiers (UPI's). A master list of key linking identifiers for both patients

and participants will be kept on a password protected file on the OUH secure Trust Network Server. Only completely anonymised data will be used outside of OUH Trust property, which will be kept on a password-protected University owned laptop or hard-drive. We plan on keeping study data for a period of 5 years following completion on the study (up to December 2026), before securely disposing of it. We believe that this storage is appropriate as the core content is scientific research data and is therefore in the public interest. Furthermore, we will require access to this data in the case of individuals wishing to scrutinise the scientific methodology, results, or conclusions of our study.

Intra-Operative Data

Raw data will be produced from the wireless sensors. Please see section 12.3 for further details regarding the recording, transfer, and storage of this data.

Other 'personal data'

1) Electronic Patient Record Data

The following data will be obtained from the NHS Electronic Patient Records (EPR), which includes the Insignia Picture Archiving and Communication System (PACS), and the Theatre Management System (TMS):

- X-ray (radiograph) analysis.
- Theatre time usage.
- Blood test & transfusion rate analysis.
- Peri-operative morbidity (30 day).
- In-patient length of stay.
- Patient demographics (age, gender, BMI)

2) Questionnaire Data

Patient Questionnaire Data

The patient questionnaires consist of the following components:

- Patient Reported Outcome Measures: The OHS and EQ-5D.

Participant (Medical Health Professionals) Questionnaire Data

Written assessments of intra-operative performance will be conducted shortly after completion of a recorded THR. These assessments may include: Global Rating Scales (GRS), Objective Structured Assessment of Technical Skills (OSATS), and surgical checklists. The data collected from these will be anonymised as it will be linked with the UPI, and not provide any names or other personal information. The hard copies will be transcribed into digital format as soon as possible, which will be stored onto a password protected encrypted file on a University owned computer/hard-drive. The hard copies of the forms will then be disposed of.

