12.6 Data Recording and Record Keeping

Intra-operative data

Motion Data

Anonymised non-personal raw motion data from the motion sensors will be wirelessly uploaded to secure off-site servers using SSL/TLS using strong cipher suites that support perfect forward secrecy. This prevents decoding of captured data, even if the secret long-term key itself is compromised. Every instance has a built-in firewall that is configured using a least privilege basis and will only accept https (port 443) connections from the internet. The data centres are staffed 24x7 by trained security guards and access is authorised strictly on a least privileged basis. Usable output motion analysis metrics will be downloaded from the secure server and stored locally on an Excel spreadsheet (.xlsx) or similar software. These data may be opened in other programmes or copied to other formats for certain analyses e.g. SPSS data files (.sav). Where study data are generated in a proprietary file type, these will be transposed to Excel format or similar.

Electronic Patient Record Data

The routine patient data will be accessed via their unique Hospital/NHS number on the recruiting NHS Trusts computer system. Following identification, the minimum dataset required (outlined previously) will be extracted by manually transcribing it directly onto a password protected encrypted file on a University owned computer/hard-drive. The data within this file will be anonymised using the UPI, and cannot be linked to any patient directly. No patient identifiable data will be directly transferred or saved from the recruiting NHS Trusts computer system.

Patient & Participant Questionnaire Data

Data from the hard copies of each questionnaire (detailed above) will be transcribed into digital format as soon as possible, which will be stored onto a password protected encrypted file on a University owned computer/hard-drive. The hard copies of the forms will then be disposed of. As they will not contain any personal data they will not have to be securely disposed of (confidential waste bins/shredding).

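### Blood loss is specified only by haemoglobin levels and compared without adjustment, although the plan already collects the pre-operative haemoglobin, sex and BMI that would give a cleaner comparison

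*Combined protocol and SAP*

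**What the plan says.** Section 6 lists "Blood loss and transfusion rates" among the patient outcomes under both the primary and the secondary objectives. The primary objective is "To assess the impact of simulation training on surgical trainee performance and patient outcomes following THR".

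Section 11 (Other outcomes data) identifies the measure only as "Blood loss (pre-/post-op haemoglobin levels". It does not say whether the analysed quantity is the post-operative level, the change, the percentage change or an estimated volume.

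For the comparison, section 11 states: "Statistical analyses between each group of participants will be performed using either the parametric unpaired t-test or a non-parametric Mann-Whitney U test". A normality check decides which of the two is used. For the registrar sub-groups it names a paired t-test or Mann-Whitney U test. None of these carries a covariate.

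Section 12 lists "Patient demographics (age, gender, BMI" among the items taken from the electronic record, but no stated analysis uses them. Height and weight are not listed, and section 12.6 confines extraction to the listed items: "the minimum dataset required (outlined previously) will be extracted by manually transcribing it". Section 8.2 sets no limit on patient size. Section 9.7 has the supervising Consultant confirm which cases on a list the registrar or Fellow will perform.

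**The concern.** The haemoglobin fall mixes what was lost at operation with who the patient is. A small patient has less blood, so the same loss removes a larger fraction of it. A higher starting haemoglobin makes the same fractional loss a larger absolute fall. Neither has anything to do with the surgeon.

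Two things are at stake. First, patient size and starting haemoglobin add avoidable variance to a comparison of 12-16 registrars with about eight patients each. Second, patients reach surgeons through waiting lists and the Consultant's confirmation of cases, not by randomisation. If sex or size mix differs between groups, part of that difference will appear as a difference in blood loss. The registrar arms have some protection, because the registrars are randomised. Registrars versus Experts and Fellows have none. Because the derived quantity is undefined, the choice between level, change and percentage change is also open until the data are seen.

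**Working it through.** **The plan's own figures.** The documents give no blood-loss mean, SD or target difference, so there is none to reproduce. The patient count agrees: 16 × 8 + 8 × 5 + 5 × 5 = 128 + 40 + 25 = 193 ("8 patients per Specialty Registrar (n = 128"; "Estimated total n= 193"). With eight registrars per arm, the randomised comparison has 64 v 64 patients.

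**Step 1: one patient.** Fall = Hb0 × (1 − exp(−L / BV)), where Hb0 is starting haemoglobin, L the loss and BV the blood volume. Assumptions, not from the documents: 65 mL/kg in women, 70 mL/kg in men, L = 1.0 L, Hb0 = 130 g/L.

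| Patient | BV (L) | Fall (g/L) |
|---|---|---|
| 50 kg woman | 3.25 | 34 |
| 70 kg woman | 4.55 | 26 |
| 85 kg man | 5.95 | 20 |
| 100 kg man | 7.00 | 17 |

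The extremes differ twofold (34 / 17). With sex-specific starting values (131 g/L in women, 145 in men, also assumed), the same two patients fall by 34.7 and 19.3 g/L, a ratio of 1.80.

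**Step 2: pairs of patients.** For losses of 0.5-1.5 L at a common Hb0 of 135 g/L, under linear or exponential dilution, the ratio of falls is 1.31-1.38 for 4.0 v 5.5 L of blood, 1.58-1.71 for 3.5 v 6.0 L, and 1.78-2.00 for 3.0 v 6.0 L.

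**Step 3: chance differences between arms.** Assume BV 4.1 L (SD 0.55) in women and 5.3 L (SD 0.7) in men, and 40.2% men (the registry share in section 5). Size alone then gives the fall a CV of 18.6%. The ratio of two arm means varies by 1.96 × 0.186 × √(2/64) = 0.064, about ±6%. With loss CVs of 30-40%, the simulated t-test rejects in 4-5% of trials when the arms have the same expected mix. For one surgeon's mean, size alone gives a standard error of 0.186 / √8 = 7% with eight patients and 0.186 / √5 = 8% with five.

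**Step 4: differing mix.** With equal true loss and a common starting haemoglobin, mean falls differ by about 5% at 30% v 50% men and about 10% at 20% v 60% men. False rejection at 64 v 64 is then 10-13% and 26-38%. Allowing men a higher starting haemoglobin offsets part of this and brings the bias down to about 2-5%. The overall range is therefore 2-10%.

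**Step 5: noise with balanced groups.** Simulation of a 20% lower loss, with assumed weights of 74 (SD 13) kg in women and 87 (SD 14) kg in men, and a volume estimate carrying 10% error in BV. Against that estimate, the unadjusted fall gives up about 3-18% of the standardised effect, most when the loss CV is 30% and haemoglobin is error-free. With a haemoglobin error SD of 8 g/L the shortfall is about 3-6%. Another run, with a within-sex haemoglobin SD of 10 g/L, gave 13%, 8% and 4% at loss CVs of 30%, 40% and 50% without error, and 3%, 3% and 2% with an error SD of 8 g/L.

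**Step 6: adjustment or formula?** At a loss CV of 40% and an error SD of 5 g/L, the standardised effects are 0.442 (unadjusted fall), 0.466 (volume estimate) and 0.463 (fall adjusted for pre-operative haemoglobin, sex and BMI). The adjustment recovers (0.463 − 0.442) / (0.466 − 0.442) = 0.021 / 0.024, or nearly 90% of the gain.

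None of these simulations includes clustering by surgeon.

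**The case against.** The strongest reply is that the plan names a data source and contains no wrong rule. Haemoglobin fall is a usable patient outcome in its own right. The tests compare groups, not pairs of patients, and chance differences in size leave the false-positive rate at its nominal level. No passage suggests that cases are chosen by body size. A volume formula shares the same post-operative sample, so fluid dilution and sampling error affect it too: at a loss CV of 40% with 8 g/L haemoglobin error, R² for true loss is 0.45 for the raw fall and 0.50 for the volume estimate. All of this stands, and it limits the size of the point.

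A reader might go further in three ways that the documents do not support:

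- That the plan scores blood loss by the raw fall. It does not say so; the derivation is left open.
- That a twofold patient-level ratio means a twofold error in the result. Twofold describes extreme pairs under assumed blood volumes. Group means move by a few per cent.
- That patient size would be read as surgeon performance. In the group comparison, size is noise unless the mix differs, and the documents show only that it could differ.

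Nor does the absence of height and weight leave the comparison beyond repair. BMI alone cannot give blood volume: at BMI 28, a height of 1.50 m means 28 × 1.50² = 63 kg and 1.90 m means 28 × 1.90² = 101 kg. As a covariate alongside sex and pre-operative haemoglobin, it is still useful.

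The objection does not remove the point that the measure is undefined and that relevant covariates are collected but left unused.

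**Conclusion.** The point holds as a minor one. The planned comparison is noisier than it needs to be, by roughly 3-18% of the standardised effect and towards the low end once realistic haemoglobin error is allowed. It is open to a bias of about 2-10% if sex or size mix differs between groups. Registrars versus Experts and Fellows is the most exposed comparison. Between the registrar arms, an imbalance would have to arise by chance among few surgeons or through the choice of cases.

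Every size quoted rests on assumed blood volumes, weights, starting haemoglobin, loss variability and measurement error. The share of the gain recovered by adjustment also depends on how closely BMI tracks body weight within each sex. The direction of the conclusion does not depend on the exact values: for a given loss, the fall depends on patient characteristics that the planned tests ignore. Blood loss is one of many unranked outcomes, which is a further reason to keep the severity low.

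**What to change.** In section 11, define the measure as the change from pre- to post-operative haemoglobin. Compare groups with a linear model for that change, adjusting for pre-operative haemoglobin, sex and BMI. Name this model in place of the t-test or Mann-Whitney U test for this outcome, and say what will be done if the residuals are clearly skewed.

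This costs a sentence or two. All three covariates are already in the plan (sections 11 and 12), so it needs no new patients, tests or data fields.

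Optionally, add height and weight to the section 12 list and report estimated volume lost as a supporting analysis: blood volume from a named published formula × ln(pre-operative Hb / post-operative Hb). This adds two fields to a manual extraction, so they should be listed before extraction begins. Its small downside is reliance on a blood-volume formula, which is why it is better as support than as the main measure.

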12 DATA MANAGEMENT

Within this study both patients and participants will have all of their personal data anonymised via the use of Unique Patient or Participant Identifiers (UPI's). A master list of key linking identifiers for both patients

and participants will be kept on a password protected file on the OUH secure Trust Network Server. Only completely anonymised data will be used outside of OUH Trust property, which will be kept on a password-protected University owned laptop or hard-drive. We plan on keeping study data for a period of 5 years following completion on the study (up to December 2026), before securely disposing of it. We believe that this storage is appropriate as the core content is scientific research data and is therefore in the public interest. Furthermore, we will require access to this data in the case of individuals wishing to scrutinise the scientific methodology, results, or conclusions of our study.

Intra-Operative Data

Raw data will be produced from the wireless sensors. Please see section 12.3 for further details regarding the recording, transfer, and storage of this data.

Other 'personal data'

1) Electronic Patient Record Data

The following data will be obtained from the NHS Electronic Patient Records (EPR), which includes the Insignia Picture Archiving and Communication System (PACS), and the Theatre Management System (TMS):

- X-ray (radiograph) analysis.
- Theatre time usage.
- Blood test & transfusion rate analysis.
- Peri-operative morbidity (30 day).
- In-patient length of stay.
- Patient demographics (age, gender, BMI)

2) Questionnaire Data

Patient Questionnaire Data

The patient questionnaires consist of the following components:

- Patient Reported Outcome Measures: The OHS and EQ-5D.

Participant (Medical Health Professionals) Questionnaire Data

Written assessments of intra-operative performance will be conducted shortly after completion of a recorded THR. These assessments may include: Global Rating Scales (GRS), Objective Structured Assessment of Technical Skills (OSATS), and surgical checklists. The data collected from these will be anonymised as it will be linked with the UPI, and not provide any names or other personal information. The hard copies will be transcribed into digital format as soon as possible, which will be stored onto a password protected encrypted file on a University owned computer/hard-drive. The hard copies of the forms will then be disposed of.

12.4 Source Data

Please see section 12 on Data management for further details. In general, the source data is as follows:

Intra-Operative Data

- Wireless motion data.
- Global rating scales and checklists.

Hospital Records Data

- NHS EPR for laboratory and clinical data.

- Insignia PACS for radiograph (x-ray) analysis.
- TMS for theatre lists, workflow, and productivity information.

Questionnaire Data

- PROMs questionnaire forms to be completed pre- and post-op (as detailed above).
- Participant performance assessment tools and feedback forms.

All confidential data will be stored securely. On all study-specific documents, other than the signed consent, the participant and patients will be referred to by the study UPI, and not by name.

12.5 Access to Data

OOSEC research team members will have access to the raw motion data. This can be matched to other metrics during the THR surgery through the use of Unique Participant Identifiers (UPI).

Direct access to the data generated from this study will be granted to authorised representatives (for example the Data Protection Officer, Caldicott Guardian, or Information Governance Team) from the sponsor and host institution for monitoring and/or audit of the study to ensure compliance with regulations.

12.6 Data Recording and Record Keeping

Intra-operative data

Motion Data

Anonymised non-personal raw motion data from the motion sensors will be wirelessly uploaded to secure off-site servers using SSL/TLS using strong cipher suites that support perfect forward secrecy. This prevents decoding of captured data, even if the secret long-term key itself is compromised. Every instance has a built-in firewall that is configured using a least privilege basis and will only accept https (port 443) connections from the internet. The data centres are staffed 24x7 by trained security guards and access is authorised strictly on a least privileged basis. Usable output motion analysis metrics will be downloaded from the secure server and stored locally on an Excel spreadsheet (.xlsx) or similar software. These data may be opened in other programmes or copied to other formats for certain analyses e.g. SPSS data files (.sav). Where study data are generated in a proprietary file type, these will be transposed to Excel format or similar.

Electronic Patient Record Data

The routine patient data will be accessed via their unique Hospital/NHS number on the recruiting NHS Trusts computer system. Following identification, the minimum dataset required (outlined previously) will be extracted by manually transcribing it directly onto a password protected encrypted file on a University owned computer/hard-drive. The data within this file will be anonymised using the UPI, and cannot be linked to any patient directly. No patient identifiable data will be directly transferred or saved from the recruiting NHS Trusts computer system.

Patient & Participant Questionnaire Data

Data from the hard copies of each questionnaire (detailed above) will be transcribed into digital format as soon as possible, which will be stored onto a password protected encrypted file on a University owned computer/hard-drive. The hard copies of the forms will then be disposed of. As they will not contain any personal data they will not have to be securely disposed of (confidential waste bins/shredding).

